## 3.8 INTERIM ANALYSES

No interim analysis is planned.

## 3.9 CHANGES TO PROTOCOL-PLANNED ANALYSES

This section summarizes major statistical changes in the protocol amendment(s).

**Table 7 - Major statistical changes in protocol amendment(s)**

Amendment Number	Approval Date	Changes	Rationale
1	08-Jul-2021	
Addition of a secondary objective and related endpoints in Part A (at Weeks 24 and 52) as follows:
 
Objective: To evaluate the effect of dupilumab in the subgroup of participants with screening blood eosinophil count <math>\geq 300</math> cells/mm<math>^3</math> compared to placebo
 
Endpoints:
 

-Change from baseline to Weeks 24 and 52 (Part A) in opacification of sinuses assessed by CT scan using LMK score in the screening blood eosinophil count <math>\geq 300</math> cells/mm<math>^3</math> population.

-Change from baseline to Weeks 24 and 52 (Part A) in sinus total symptom score (sTSS) using the screening blood eosinophil count <math>\geq 300</math> cells/mm<math>^3</math> population.

-Evaluation of other secondary endpoints listed above in the screening blood eosinophil count <math>\geq 300</math> cells/mm<math>^3</math> population.

	To evaluate the effect of dupilumab in a subgroup of interest as the primary analysis population was changed to the ITT population regardless of eosinophil levels in Part A, per Health Authority request.
		
The primary efficacy analysis population was changed from ITT population with screening blood eosinophil count <math>\geq 300</math> cells/mm<math>^3</math> to ITT population for Part A.
 
Intercurrent event handling strategy for prohibited medications added in Table 7.
	Per Health Authority request for Part A
		
Power calculations updated for Part A. Screening blood eosinophil count added as covariate in model-based analyses for Part A.
	To reflect change in the primary efficacy analysis population
		
Multiplicity considerations updated
	
		
Intercurrent event handling strategy for undergoing sinonasal surgery for CRSsNP prior to Week 24 was changed from "data after surgery will be assigned to the worst possible score (composite strategy)" to "Data
	To change handling of sinonasal surgery in the primary estimand to an approach more appropriate for

Amendment Number	Approval Date	Changes	Rationale
		
collected after surgery will be set to missing and the worst post-baseline value on or before the time of surgery will be used to impute missing Week 24 value (WOCF). For participants with no post-baseline values, the baseline value will be used (hypothetical strategy)."
 
Sensitivity/supplementary analyses updated
	this clinical setting and to update supplementary analyses accordingly
2	23-Feb-2023	
Sample size determination updated.
 
Primary population changed from ITT population to ITT population with screening blood eosinophil count <math>\geq 300</math> cells/mm^3.
 
Statistical hypotheses removed.
 
Multiplicity consideration removed.
 
Multiple imputation removed.
 
Model-based analyses removed.
 
Sensitivity and subgroup analyses removed.
 
Use of descriptive statistics for all endpoints.
	To reflect changes in the study primary objective and endpoint.
		
The intercurrent events handling strategy for taking SCS for any reason prior to Week 24 was changed from 'all data collected after SCS use will be used in the analysis' to 'data after the IE will be set to missing and the worst post-baseline value on or before the time of the IE will be used to impute missing Week 24 value (WOCF)'.
	To change handling of taking SCS for any reason in the primary estimand to an approach more appropriate for this clinical setting.
		
Description of secondary analyses for proportion and time-to-event endpoints removed.
	To reflect changes in the secondary objectives and endpoints.
		
Updated the timing of analyses to only one database lock after all participants have completed the study.
	To reflect the removal of Part B and shortened treatment duration of Part A.

## 4 SAMPLE SIZE DETERMINATION

Sample size calculation was performed to ensure reasonable accuracy for the estimation of the primary endpoint in participants treated with dupilumab with screening blood eosinophil count  $\geq 300$  cells/mm $^3$ . With a 1:1 randomization ratio, a standard deviation (SD) of 5 and a dropout rate of 10%, a sample size of approximately 30 participants (15 per arm) with screening blood eosinophil count  $\geq 300$  cells/mm $^3$  will provide a half-width of approximately less than 3 for the 2-sided 95% CI in the dupilumab group which is deemed reasonable.

In addition, it is planned to include approximately 40 participants (20 per arm) with screening blood eosinophil count  $< 300$  cells/mm $^3$ . Thus, the planned total sample size is approximately 35 participants per arm.

## 5 SUPPORTING DOCUMENTATION

### 5.1 APPENDIX 1 LIST OF ABBREVIATIONS

ACQ-6:	asthma control questionnaire-6 items
ADA:	anti-drug antibody
AE:	adverse event
AESIs:	adverse events of special interest
ALT:	alanine aminotransferase
ATC:	anatomic category
CI:	confidence interval
CLcr:	Creatinine clearance
CRSsNP:	chronic rhinosinusitis without nasal polyposis
CT:	computerized tomography
CV:	coefficient of variation
e-CRF:	electronic case report form
EOS:	End of Study
FEV 1 :	forced expiratory volume
HLT:	high level term
HRQoL:	health-related quality of life
IEs:	intercurrent events
IMP:	investigational medicinal product
INCS:	intranasal corticosteroids
IRT:	Interactive Response Technology
ITT:	intent-to-treat
LLOQ:	lower limit of quantification
LLT:	lower-level term
LMK:	Lund-Mackay
MedDRA:	medical dictionary for regulatory activities
NAb:	neutralizing antibody
NC:	nasal congestion
NES:	Normalized Enrichment Score
PCSA:	potentially clinically significant abnormality
PGIC:	Patient Global Impression of Change
PGIS:	Patient Global Impression of Severity
PK:	pharmacokinetics
PT:	preferred term
SCS:	systemic corticosteroids
SD:	standard deviation
SEM:	standard error of the mean
SMQ:	standardized MedDRA query
SNOT-22:	Sino-Nasal Outcomes Test-22 item
SOC:	system organ class
STSS:	sinus total symptom score

TE:	treatment-emergent
TEAE:	treatment-emergent adverse event
TESAEs:	treatment-emergent serious adverse events
ULN:	upper limit of normal
ULOQ:	upper limit of quantification
UPSTIT:	University of Pennsylvania smell identification test
VAS:	visual analog scale
WHO-DD:	World Health Organization-drug dictionary
WOCF:	worst observation carried forward

## 5.2 APPENDIX 2 PARTICIPANT DISPOSITIONS

The number (%) of participants included in each of the analysis populations listed in [Table 3](#) will be summarized.

Screen failures are defined as participants who consent to participate in the study but are not subsequently randomized. The number (%) of screen failures and reasons for screen failures will be provided in the screened population.

The number (%) of participants in the following categories will be provided:

- Randomized participants
- Randomized but not exposed participants
- Randomized and exposed participants
- Participants who completed the study treatment period as per protocol
- Participants who did not complete the study treatment period as per protocol and main reason for permanent intervention discontinuation.
- Participants who completed the study period as per protocol.
- Participants who did not complete the study period as per protocol and main reason for study discontinuation.

Reasons for permanent study intervention and study discontinuation “adverse event” and “other reasons” will be split as related versus not related to the COVID-19 pandemic, if applicable.

The number (%) of exposed and not randomized participants will also be summarized.

In addition, the number (%) of participants screened, screened-failed, randomized, with permanent intervention discontinuation and with early study discontinuation will be provided by country and site.

### Protocol deviations

Critical and major protocol deviations (automatic or manual) will be summarized in the randomized population as well as displayed separately as related versus not related to the COVID-19 pandemic if applicable. In addition, deviations potentially impacting the primary endpoint analysis may be summarized.

## **5.3 APPENDIX 3 DEMOGRAPHICS AND BASELINE CHARACTERISTICS, PRIOR OR CONCOMITANT MEDICATIONS**

### *Demographics, baseline characteristics, medical surgical history*

The following demographics and baseline characteristics, medical and surgical history and disease characteristics at baseline will be summarized using descriptive statistics in the randomized population.

Demographic variables are:

- Age in years as quantitative variable and in categories (18-<65, 65 - <75, 75 - <85 and  $\geq 85$  years)
- Gender (Male, Female)
- Race (White, Black or African American, American Indian or Alaska Native, Asian, Native Hawaiian or other Pacific Island, Multiple, Not reported, Unknown)
- Ethnicity (Hispanic or Latino, not Hispanic or Latino, Not Reported, Unknown)
- Region (**Asia**: China, South Korea; **Latin America**: Argentina, Chile; **East Europe**: Hungary, Russia, Ukraine; **Western Countries**: Belgium, Canada, Portugal, Spain, Sweden, USA)
- Territory (**North America**: Canada, USA; **European Union**: Belgium, Hungary, Spain, Portugal, Sweden; **Rest of World**: Argentina, Chile, China, South Korea, Russia, Ukraine)
- Weight in kg as quantitative variable
- BMI in kg/m^2 as quantitative variable and in categories (<25,  $\geq 25$ -<30,  $\geq 30$  kg/m^2)

Baseline safety and efficacy parameters (apart from those listed above) will be presented along with the safety and efficacy summaries.

Medical (or surgical) history includes all the relevant medical (or surgical) history during the lifetime of the participant. Medical and surgical history will be coded to a LLT, PT, HLT, HLGT, and associated primary SOC using the MedDRA version currently in effect at Sanofi at the time of database lock.

CRSSNP and allergic comorbidities will be summarized separately. The following comorbid disease will be summarized from eCRF pages which were filled in by investigators based on participant reporting.

- Chronic rhinosinusitis without nasal polyps (Yes, Ongoing condition)
- Posterior nasal drip (Yes, Ongoing condition)
- Diminished sense of smell (Yes, Ongoing condition)
- Nasal congestion (Yes, Ongoing condition)
- Nasal discharge (Yes, Ongoing condition)
- Nasal polyps (Yes, Ongoing condition)
- Facial pain/pressure (Yes, Ongoing condition)
- Seasonal allergic rhinitis (Yes, Ongoing condition)
- Perennial allergic rhinitis (Yes, Ongoing condition)
- Allergic rhinitis (Yes, Ongoing condition)
- Allergic conjunctivitis (Yes, Ongoing condition)
- Atopic dermatitis (Yes, Ongoing condition)
- Epistaxis (Yes, Ongoing condition)
- Aspirin-exacerbated respiratory disease (Yes, Ongoing condition)
- Hives (Yes, Ongoing condition)
- Eosinophilic esophagitis (Yes, Ongoing condition)
- Egg allergy (Yes, Ongoing condition)
- Fish allergy (Yes, Ongoing condition)
- Milk allergy (Yes, Ongoing condition)
- Peanut allergy (Yes, Ongoing condition)
- Allergy to nuts (Yes, Ongoing condition)
- Shellfish allergy (Yes, Ongoing condition)
- Soy allergy (Yes, Ongoing condition)
- Flour sensitivity (Yes, Ongoing condition)
- Gluten sensitivity (Yes, Ongoing condition)

Prior sinonasal surgery and systemic corticosteroid history will be summarized as below.

- Number of participants with prior sinonasal surgery and/or SCS use in the past 2 years before screening visit
- Number of participants with prior sinonasal surgery

- Number of prior sinonasal surgeries (quantitative and in categories of 1 or  $\geq 2$ )
- Number of participants with prior sinonasal surgery by type
- Time since most recent sinonasal surgery (years)
- Number of participants with SCS use in the past 2 years before screening visit
- Number of SCS courses in the past 2 years before screening visit (quantitative and in categories of 1, 2, 3, 4,  $\geq 5$ )
- Number of days with SCS use in the past 2 years before screening visit (quantitative and in categories of  $>0 - \leq 7$ ,  $>7 - \leq 14$ ,  $>14 - \leq 21$ ,  $>21 - \leq 28$ ,  $>28 - \leq 56$ ,  $>56 - \leq 84$ ,  $>84 - \leq 112$ ,  $>112$ )

In addition, asthma history will be summarized for participants with comorbid asthma:

- Age at asthma onset (years)
- Time since first diagnosis of asthma (years)

### ***Disease characteristics at baseline***

The following baseline disease characteristics will be summarized by intervention group:

- Age at onset of CRSsNP (years)
- Time since first diagnosis of CRSsNP (years)
- Baseline LMK score
- Baseline sTSS
- Baseline 3-dimensional CT volumetric measurement of the paranasal sinuses
- Baseline nasal congestion/obstruction score
- Baseline anterior/posterior rhinorrhea score
- Baseline facial pain/pressure severity score
- Baseline loss of smell symptom severity score
- Baseline headache severity score
- Baseline UPSIT score
- Baseline SNOT-22 score
- Baseline rhinosinusitis VAS score
- Baseline EQ-VAS score
- Baseline EQ-5D-5L single index score
- Baseline PGIS score
- Comorbid asthma (Yes, No)

- Baseline FEV1 (L)
- Baseline FEV1 percent predicted (%)
- Baseline ACQ-6 score in participants with comorbid asthma
- Background INCS use
- Smoking history (Never, Former, Current)
- Frequency of alcohol drinking in the past 12 months (never, occasional, at least monthly, at least weekly, at least daily) and number of drinks on a typical day (1 or 2,  $>2$ )
- Screening blood eosinophil count ( $10^9/L$ )
- Screening blood eosinophil count category ( $<0.3$ ,  $\geq 0.3 \times 10^9/L$ )

### ***Prior or concomitant medications***

All medications will be coded using the World Health Organization-Drug Dictionary (WHO-DD) using the version currently in effect at Sanofi at the time of database lock.

- Prior medications are those the participant received prior to first IMP intake. Prior medications can be discontinued before first administration or can be ongoing during treatment period.
- Concomitant medications are any interventions received by the participant concomitantly to the IMP, from first administration of IMP to last IMP intake + 98 days.
- Post-treatment medications are those the participant received in the period running from the end of the concomitant medications period up to the end of the study.
- A given medication can be classified as a prior medication and/or as a concomitant medication and/or as post-treatment medication. If it cannot be determined whether a given medication was taken prior or concomitantly or post, it will be considered as prior, concomitant, and post-treatment medication.

The prior and concomitant medications will be summarized for the randomized population.

Medications will be summarized by intervention group according to the WHO-DD dictionary, considering the first digit of the anatomic category (ATC) class (anatomic category) and the first 3 digits of the ATC class (therapeutic category). All ATC codes corresponding to a medication will be summarized, and participants will be counted once in each ATC category (anatomic or therapeutic) linked to the medication. Therefore, participants may be counted several times for the same medication.

The tables for prior medications will be sorted by decreasing frequency of ATC followed by all other therapeutic classes based on the overall incidence across intervention groups. In case of equal frequency regarding ATCs (anatomic or therapeutic categories), alphabetical order will be used.

Concomitant medication received between the first IMP to last IMP +14 days and concomitant medication received between the first IMP to last IMP + 98 days will be summarized separately. The tables for concomitant medications will be sorted by decreasing frequency of ATC followed by all other therapeutic classes based on the incidence in the dupilumab group. In case of equal frequency regarding ATCs (anatomic or therapeutic categories), alphabetical order will be used.

## 5.4 APPENDIX 4 DATA HANDLING CONVENTIONS

### Demographic formulas

Age at onset of CRSsNP (years):

$$\text{Year of first diagnosis of CRSsNP} - \text{Year of birth}$$

Time since first diagnosis of CRSsNP (years):

$$(\text{Year of randomization} - \text{Year of first diagnosis of CRSsNP}) + \\ (\text{Month of randomization} - \text{Month of first diagnosis of CRSsNP})/12$$

Time since most recent sinonasal surgery (years):

$(\text{Date of randomization} - \text{Date of most recent sinonasal surgery})/365.25$  if a complete date of most recent sinonasal is available;

$(\text{Year of randomization} - \text{Year of most recent sinonasal surgery}) + (\text{Month of randomization} - \text{Month of most recent sinonasal surgery})/12$  if year and month are available;

$(\text{Year of randomization} - \text{Year of most recent sinonasal surgery})$  if only year is available

Age at onset of asthma (years):

$$\text{Year of first diagnosis of asthma} - \text{Year of birth}$$

Time since first diagnosis of asthma (years):

$$(\text{Year of randomization} - \text{Year of first diagnosis of asthma}) + \\ (\text{Month of randomization} - \text{Month of first diagnosis of asthma})/12$$

BMI is calculated as:

$$\text{Weight in kg} / (\text{height}^2 \text{ in meters})$$

### Renal function formulas

For adults, creatinine clearance (CLcr) value will be derived using the equation of Cockcroft and Gault:

$$\text{CLcr (ml/min)} = (140 - \text{age}) \times \text{weight (kg)} \times (1 - 0.15 \times \text{sex (0-M, 1-F)}) / (0.814 \times \text{creatinine} \text{ (} \mu\text{mol/L}\text{)})$$

For participants <18 years old, CLcr value will be derived using the equation of GFR Bedside Schwartz

$$\text{GFR (mL/min/1.73 m}^2\text{)} = k \times \text{height (cm)} / \text{sCr (mg/dL)},$$

where the coefficient  $k = 0.65$  for male adolescent participants or  $k = 0.55$  for female adolescent participants

CLcr will be calculated using the last weight measurement on or before the visit of the creatinine measurement and age at the lab sampling day. Here age is calculated as following:

$$\text{Age} = \text{age collected at screening} + \text{integer part of (lab sampling analysis day / 365.25)}$$

### **Normalization of nasal secretion and urine biomarkers**

Nasal secretion biomarkers will be normalized with total protein as the reference. Urine biomarkers will be normalized with creatinine as the reference. For example,

$$\text{normalized Tryptase (ug/mg)} = \text{Tryptase (ug/L)} / \text{Total protein (ug/mL)}$$

$$\text{normalized Leukotriene E4 (ng/mg)} = \text{Leukotriene E4 (ng/mg)} / \text{Creatinine (mg /mL)}$$

### **Daily e-diary weekly scores**

For the daily efficacy endpoints (sTSS, NC, rhinorrhea, facial pain/pressure, loss of smell and headache), the time period used to calculate the periodical average score at each designated study day is summarized in [Table 8](#). Randomization day is used as the reference day (Day 1).

**Table 8 - Periodical average of daily efficacy assessment from e-diary**

Analysis visit	Target day	Day range for calculating periodical average score
Week 4	29	2-29
Week 8	57	30-57
Week 12	85	58-85
Week 16	113	86-113
Week 20	141	114-141
Week 24	169	142-169
Week 28	197	170-197
Week 32	225	198-225
Week 36	253	226-253
Week 40	281	254-281
Week 44	309	282-309
Week 48	337	310-337

Analysis visit	Target day	Day range for calculating periodical average score
Week 52	365	338-d
EOT + 4 weeks	29*	2-29*
EOT + 8 weeks	57*	30-57*
EOT + 12 weeks	85*	58-85*

d: planned EOT date, EOT: End of Treatment, EOS: End of Study

\* Relative to d

## Analysis windows for time points

For the safety assessment, the reference date for the derivation of relative days of events or findings will be the date of first IMP administration. Selected safety variables will be summarized by the analysis window defined in [Table 9](#) for the by visit descriptive analysis. All available values from central lab will be assigned to the appropriate visit window. In the event of multiple measurements of the same test in the same window, the one closest to the targeted visit date will be used for the by-visit summary. If they are at the same number of days away from the target day, the latest one will be used. For procedures planned on Visit 2, if it is done on the same date as the first IMP injection but the performance time is missing, it will belong to the Visit 2 window.

**Table 9 - Time window for safety endpoints**

Analysis visit	Target day	Time windows for		
		Vital signs	Laboratory (hematology, chemistry, urinalysis)	Urine pregnancy
Screening	-28 to -14	<-14	<-14	
Baseline	1	-14-1-	-14-1-	14-1-
Week 2	15	1*-49		
Week 4	29			1*-42
Week 8	57			43-70
Week 12	85	50-126	1*-126	71-98
Week 16	113			99-126
Week 20	141			127-154
Week 24	169	127-224	127-224	155-182
Week 28	197			183-210
Week 32	225			211-238
Week 36	253			239-266
Week 40	281	225-322	225-322	267-294
Week 44	309			295-322
Week 48	337			323-350
Week 52	365	>322	>322	>350

1:: up to 1st dose date/time; 1+: after 1st dose date/time;

For the efficacy assessment, the reference date for the derivation of relative days of events or findings will be the randomization day. If a participant receives IMP prior to the randomization by mistake, the reference date of efficacy assessment will be the date of the first IMP administration for that participant. For the primary analyses, all available values of scheduled measurements will be assigned to the appropriate visit window according to [Table 10](#). In the event of multiple measurements of the same test in the same window, the one closest to the targeted visit date will be used for the by-visit summary. If they are at the same number of days away from the target day, the latest one will be used.

**Table 10 - Time window for efficacy variables**

Analysis visit	Target day	Time windows for							
		LMK /3-D CT	UPSiT, VAS	SNOT-22	Spirometry	ACQ-6	EQ-5D-5L	PGIS, HCRU/P	PGIC
Screening	-28 to -14				<14				
Baseline	1	<1-	<1-	<1-	-14-1-	1-	1-	<1-	
Week 2	15		1*-91						
Week 12	85				1*-126	1*-126		1*-126	1*-126
Week 24	169	1*-266	92-224	1*-224	127-266	127-224	1*-224	127-224	127-224
Week 40	281		225-322	225-322		225-322	225-322	225-322	225-322
Week 52	365	267-d	323-d	323-d	267-d	323-d	323-d	323-d	323-d
EOS*	NA		NA	NA	NA	NA			

d: planned EOT date, EOT: End of Treatment, EOS: End of Study

1-: up to randomization and before 1st dose date/time; 1\*: after randomization or 1st dose date/time

\* Data collected at the EOS visit will not be remapped

For the pharmacokinetics/pharmacodynamics variables summary, the reference date for the derivation of relative days of measurements will be the date of first IMP administration if the participant is treated with study intervention, or the randomization date if the participant is not treated. Pharmacokinetics /pharmacodynamics variables will be summarized by the analysis window defined in **Table 11** for the by visit descriptive analyses. All available values of measurements will be assigned to the appropriate visit window. In the event of multiple measurements of the same test in the same window, the one closest to the targeted visit date will be used for the by-visit summary. If they are at the same number of days away from the target day, the latest one will be used. For procedures planned on Visit 2, if it is done on the same date as the first IMP injection but the performance time is missing, it will belong to the Visit 2 window.

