### 1.3 SCHEDULE OF ACTIVITIES (SOA)

Procedure	Screening (2 to 4 weeks before Day 1) D-28	Intervention Period (Weeks)						Follow-up W36 to W64 (12 weeks) a	Notes
	W0	W2	W12	W24	W40	W52			
Visit	1	2 b	3	4	5	6 a	7 (EoT) a,c	8 (EOS)	Visit window: +3 days for Visit 2, ±3 days for visits 3 to EOT, and ±5 days for EOS
Informed consent d	X								
Inclusion and exclusion criteria	X	X							Recheck clinical status before randomization
Participant demographics	X								
Full physical examination	X	X			X		X		Including skin (full body skin exam), nasal cavities, eyes, ears, respiratory, cardiovascular, gastrointestinal, neurological, lymphatic, and musculoskeletal systems
Medical/surgical history e	X								
Record planned endoscopic sinus surgery f	←————→								
Nasal endoscopy g	X								Central reading for excluding polyps and local reading for excluding purulent discharge
Prior/concomitant/rescue medications	X	X	X	X	X	X	X	X	Check INCS background medication at screening and throughout the study period. Record rescue therapy if applicable
Randomization		X							
Log-in to IRT	X	X	X	X	X	X	X	X	
Study intervention h,i									
IMP administration j			←————→						IMP will be administered every 14 ±3 days (q2w). Between visits at site home administration is allowed after

									appropriate training of the participant (or caregiver). The planned last dose is up to Week 50.
Efficacy assessmentsh									
CT scan k	X				X		X		Initial CT scan to be done during screening period, results should be available prior to randomization (Visit 2).
Dispense or download daily diary for symptoms l	X	X	X	X	X	X	X	X	Device will be dispensed at screening (including instructions for use). At EOS, the e-diary will be returned to the site.
CRSsNP Symptom Diary (includes nasal congestion/obstruction, facial pain/pressure, anterior and posterior rhinorrhea; sTSS derived from these 4 items, as well as loss of smell and headache) l,m	←----- Daily Diary -----→								Every day (morning assessment) as of screening. Participant will continue to assess daily symptoms during follow-up (important to assess disease relapse after treatment)
Sino-Nasal Outcome Test-22 item (SNOT-22) m		X			X	X	X	X	
University of Pennsylvania Smell Identification Test (UPSIT)		X	X		X	X	X	X	Baseline value to be collected ahead of first dose IMP

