ACQ-6: Asthma Control Questionnaire 6-question version, ADA: anti-drug antibody, AE: adverse event, AESI: adverse event of special interest, CRSsNP: chronic rhinosinusitis without nasal polyposis, CT: computerized tomography, COVID-19: Coronavirus Disease 2019, D: day, DBP: diastolic blood pressure, ECG: electrocardiogram, eCRF: electronic case report form, EOS: end of study, EOT: end of treatment, EQ-5D-5L: 5-level version of the EuroQol 5 dimensions European quality of life-5D scale, FEF: forced expiratory flow, FEV1: forced expiratory volume, FVC: forced vital capacity, HBcAb: hepatitis B core antibody, HBsAb: hepatitis B surface antibody, HBsAg: hepatitis B surface antigen, HBV: hepatitis B virus, HCRU/P: Healthcare Resource Utilization/Productivity, HCV: hepatitis C virus, HCVAb: hepatitis C virus antibodies, HIV: Human Immunodeficiency Virus, IEC: independent ethics committee, Ig: immunoglobulin, IRB: institutional review board, IMP: investigational medicinal product, IRT: interactive response technology, INCS: intranasal corticosteroids, LABA: long-acting beta-agonists; LAMA: long-acting muscarinic acetylcholine, LTE4: leukotriene 4, PGDM: prostaglandin D2 metabolite, PGIS: patient global impression of severity, PGIC: patient global impression of change, PK: pharmacokinetic, PRO: patient-reported outcome, q2w: every 2 weeks, SAE: serious adverse event, SBP: systolic blood pressure, SC: Subcutaneous, SCS: systemic corticosteroids, sTSS: sinus Total Symptom Score, SNOT-22: Sino-Nasal Outcome Test – 22 item, TB: tuberculosis, TARC: thymus-and activation-regulated chemokine, UPSIT: University of Pennsylvania smell identification test, VAS: visual analog scale, V: Visit, W: week, WOCBP: women of childbearing potential.

- a The treatment period will be variable between 24 to 52 weeks; therefore, follow up may be between 36 to 64 weeks. V6 and V7 are optional for participants given variable treatment period.
- b All assessments at Randomization Visit (V2) are to be conducted pre-IMP dose with the exception of the assessment of local tolerability of subcutaneous (SC) injections.

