### 3 STATISTICAL ANALYSES

#### 3.1 GENERAL CONSIDERATIONS

In general, continuous data will be summarized using the number of observations available, mean, standard deviation (SD), median, minimum, and maximum. Categorical and ordinal data will be summarized using the count and percentage of participants. The summary statistics will be provided at each visit, including data collected beyond Week 24.

The baseline value of efficacy parameters is defined as the last available value up to randomization date and prior to the first dose of study medication unless otherwise specified. The baseline value of the other parameters is defined as the last available value prior to the first dose of investigational medicinal product (IMP) if the participant is treated, or the last available value up to randomization date if the participant is not exposed to IMP.

For endpoints collected on the daily CRSsNP sinonasal symptom diary, baseline is defined as the average of the scores in the 7 days prior to randomization. If there are less than 7 but at least 4 non-missing scores available, the baseline score is the average of the available scores in the 7 days. If there are less than 4 non-missing scores, then baseline will be the average of the most recent 4 days with non-missing scores prior to randomization.

Stratification factors used in analyses will be derived based on eCRF data (for background INCS and region) or central laboratory data (for screening blood eosinophil count).

Unless otherwise specified, analyses will be performed by intervention group and overall for baseline and demographics characteristics.

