## 3.2 PRIMARY ENDPOINT ANALYSIS

### 3.2.1 Definition of endpoint

The primary endpoint is the change from baseline to Week 24 in LMK score in the dupilumab group. The LMK score is based on assessment of the CT scan findings for each sinus area (maxillary, anterior ethmoid, posterior ethmoid, sphenoid, and frontal sinus on each side). The extent of mucosal opacification is rated on a 3-point scale ranging from 0 = normal to 2 = total opacification. In addition, the ostiomeatal complex is graded as 0 = not occluded or 2 = occluded. The maximum score is therefore 12 per side for a maximum total score of 24, corresponding to the sum of all sinuses and the ostiomeatal unit.

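### SAP Table 10 closes the Week 52 efficacy windows on the planned EOT date, so a permitted EOT visit 1 to 3 days later has no window when planned EOT falls late

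*SAP*

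**What the plan says.** SAP 5.4 (Appendix 4) says, just before Table 10, that for efficacy "all available values of scheduled measurements will be assigned to the appropriate visit window according to" that table. The Week 52 row, target day first, reads "365 267-d 323-d 323-d 267-d 323-d 323-d 323-d 323-d". So the window runs from Day 267 to d for LMK/3-D CT and for spirometry, and from Day 323 to d for UPSIT/VAS, SNOT-22, ACQ-6, EQ-5D-5L, PGIS with HCRU/P, and PGIC. The footnote defines d: "d: planned EOT date, EOT: End of Treatment, EOS: End of Study". The only later row is EOS, with the note "Data collected at the EOS visit will not be remapped".

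The protocol's Schedule of Activities (section 1.3) sets the visit window at plus or minus "3 days for visits 3 to EOT, and ±5 days for EOS". It also says "The treatment period will be variable between 24 to 52 weeks", so d differs between participants.

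SAP 3.1 commits to using the late data: "The summary statistics will be provided at each visit, including data collected beyond Week 24".

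Elsewhere in SAP 5.4 the Week 52 window has no upper end. Table 9 gives >322 for vital signs and laboratory values and >350 for urine pregnancy tests. Table 11 gives >266 for serum dupilumab, ADA and biomarkers.

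**The concern.** An EOT visit on d+1, d+2 or d+3 meets the protocol, but for a participant with a late planned EOT it comes after every Table 10 window has closed. Nothing else takes it in. The EOS row is for EOS-visit data. The paragraph on unscheduled visits helps only measurements that can be re-allocated to a scheduled visit, which again needs a window.

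The same visit's laboratory, vital-sign, PK and biomarker values are kept, because Tables 9 and 11 are open-ended. SAP 3.6.1 also has an exposure category running to 52 weeks + 3 days, so the visit tolerance was foreseen there but not in Table 10.

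At stake are the Week 52 rows of the efficacy by-visit summaries. The primary analysis population is planned at about 15 participants per arm, so a few unassigned visits could visibly change n and the mean. The group is not hypothetical. The first randomization was on 24-Feb-2021, and the fixed 52-week treatment period was replaced only by the amendment of 23-Feb-2023, so participants from the first year or so had a planned EOT at 52 weeks.

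**Working it through.** **Inputs**

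- Efficacy windows: SAP Table 10, with randomization as Day 1.
- Permitted EOT days: d−3 to d+3, which is 7 days (protocol 1.3).
- Planned EOT: from Week 24 to Week 52 (protocol 1.3).
- Follow-up: 12 weeks, with ±5 days for EOS (protocol 1.3).

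**Step 1: reproduce the SAP's day count.** Target day = 7 × week + 1. Weeks 2, 12, 24, 40 and 52 give Days 15, 85, 169, 281 and 365, all as in Table 10. So d runs from about Day 169 to Day 365.

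**Step 2: a participant planned for the full 52 weeks.** Here d = 365 and the permitted EOT days are 362 to 368. Days 362 to 365 lie in the Week 52 window in all eight columns. Days 366, 367 and 368 lie in no window in any column. That is 3 of 7 permitted days.

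**Step 3: the earliest d at which a late visit can fall out.** The windows before Week 52 are not capped at d, so a late visit is safe as long as d+3 does not pass the last of them.

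- LMK/3-D CT and spirometry: the Week 24 window ends on Day 266. Safe if d + 3 ≤ 266, that is d ≤ 263. A gap is possible from d = 264.
- Other six columns: the Week 40 window ends on Day 322. Safe if d + 3 ≤ 322, that is d ≤ 319. A gap is possible from d = 320.

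**Step 4: examples**

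| Planned EOT d | LMK/3-D CT, spirometry: days with no window | Other six columns: days with no window |
|---|---|---|
| 263 | none | none |
| 264 | d+3 | none |
| 266 | d+1 to d+3 | none |
| 319 | d+1 to d+3 | none |
| 320 | d+1 to d+3 | d+3 |
| 322 | d+1 to d+3 | d+1 to d+3 |
| 365 | d+1 to d+3 | d+1 to d+3 |

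Visits on d−3 to d have a window for every d from 169 to 365 in every column.

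**Step 5: test the remedy.** With the Week 52 windows closed at d+3, no permitted EOT day is left without a window in any column, for any d from Day 169 to Day 365. An open-ended Week 52 window gives the same result. EOS is planned 12 × 7 = 84 days after EOT, so its window is d+79 to d+89. The new limit of d+3 is 76 days short of that.

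**The case against.** **d could mean the actual date of the scheduled EOT visit.** The word 'planned' might only separate that visit from an EOT visit made at premature discontinuation. Nothing would then fall out. But the footnote says planned, and a planned date is not the date on which the visit took place. What stands is that the SAP never says how d is derived for each participant under the variable treatment period, and it would help to say so.

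**No sentence says that values are discarded.** The rule is to assign all available scheduled values. That is true, but it assigns them through Table 10, and a value after d has no row to go to. Following the table leaves the value out of the Week 52 row. Keeping it would take an unplanned decision.

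**Late data carry little weight here.** Visits 6 and 7 and the Week 52 CT are optional, HCRU/P is summarized cumulatively over the treatment period, and no hypotheses are tested. This stands, and it is why the point is minor.

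**Table 8 also uses d.** It ends the Week 52 diary period at d and starts the EOT + 4 weeks period straight after. A d+3 limit in Table 10 would differ from it. This is not a real conflict, because Table 8 averages daily diary scores and Table 10 places single visit measurements, but the SAP should say so.

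**A reader might infer that safety and efficacy tables ought to show the same Week 52 attendance.** The documents do not support that. Safety summaries use the safety population and count days from first IMP. The main efficacy summaries use the ITT population with screening eosinophils ≥300 cells/mm³ and count from randomization. The argument from Tables 9 and 11 is about how windows are built, not about matching counts.

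**Conclusion.** The gap is real, and its scope is narrow. It reaches only EOT visits made 1 to 3 days after the planned date, and only when planned EOT is Day 264 or later (LMK/3-D CT, spirometry) or Day 320 or later (the other six columns). The consequence is that the visit is left out of the Week 52 by-visit descriptive summary. This rests on reading d as the footnote words it.

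Three stronger readings are tempting, and the documents support none of them.

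- *On-schedule EOT results are lost.* They are not: visits on the planned day or up to 3 days early always have a window.
- *A known share of visits is lost.* If visits were spread evenly over the 7 permitted days, 3/7 = 43% of those with d at or above the full-gap days (266 and 322) would be late. That spread is an assumption. The share could be anything from 0% (none late) to 100% (all late), and the documents give no distribution of planned EOT dates or visit delays. The number affected cannot be computed.
- *The efficacy results are affected.* SAP 3.2.1 states "The primary endpoint is the change from baseline to Week 24 in LMK score in the dupilumab group". The secondary efficacy endpoints, and the exploratory efficacy endpoints in SAP 3.4, are also at Week 24. None of them uses the Week 52 window.

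**What to change.** In SAP Table 10, replace d by d + 3 days as the upper limit in all eight Week 52 cells. Alternatively, leave the Week 52 windows open-ended and keep EOS-visit data separate, as Table 11 does for PK and ADA. Add one line saying how d is derived for each participant. Add another saying that the Table 8 diary periods, which also use d, are unchanged because they average daily scores.

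The cost is one table edit and two sentences in the SAP, best made before database lock so that no window decision is taken after the data are seen. No protocol change or extra data collection is needed.
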